7.8.3 Vital signs

Descriptive statistics over time including change from baseline will be performed for vital signs (blood pressure and pulse rate).

7.8.4 ECG

Continuous safety ECG monitoring (by investigator) – (SRD parts only)

Clinically relevant abnormal findings will be reported as adverse events.
No separate listing or analysis of continuous ECG monitoring will be prepared.

12-lead ECG (SRD parts + FE part)

Abnormal findings will be reported as baseline conditions (at screening) or as AEs (during the trial) if judged clinically relevant by the investigator.

All evaluations of ECG data will be based on the TS, except the exposure-response analyses, which are based on the ECGPCS set.

The following ECG analyses will only be performed in the SRD parts:

Listing of individual data

For all quantitative endpoints, listings of individual data will be shown in Appendix 16.2. For QTcB and RR only listings will be provided. Occurrences of notable findings will be flagged.

Comments regarding the ECGs will be listed.

Categorical endpoints

For the categorical endpoints, frequency tables will be provided.

For all subjects with any notable finding in ECG intervals, a separate listing will be created as end-of-text display (based on the same display template as in Appendix 16.2), and the corresponding time profiles will be shown.

Quantitative endpoints:

Descriptive statistics (N, mean, SD, min, median, max) will be provided for the changes from baseline over time of QTcF, HR, QT, PR and QRS. The time profiles of mean and SD for the changes from baseline on treatment will be displayed graphically by treatment.

For QTcF and HR changes from baseline the relationship to the corresponding plasma concentration is evaluated using an exposure response model.

This model will be evaluated separately for doses under fasting conditions and doses under fed conditions.

For the following analyses, all time points with available ECG endpoints and time-matched plasma concentrations of all dose groups will be included. For the handling of missing values see [Section 6.6](#).

The response variable will be the change from baseline in QTcF (Δ QTcF). The placebo subjects will be included in the analysis, setting their plasma concentrations to zero.

As a first step, it is investigated if there is a potential delayed or accelerated (e.g. metabolites) effect of the drug on QTcF. A general visual impression is provided by overlaying time profiles of plasma concentrations and QTcF changes from baseline (Δ QTcF). All figures will

be generated for each subject (presented in statistical Appendix of the CTR), as well as for means per active treatment (presented in the End-of-Text tables of the CTR).

The relationship between BI 705564 plasma concentrations and QTcF changes from baseline will be investigated in an exploratory manner using a random coefficient model approach to estimate the difference in means between BI 705564 and placebo in QTcF change from baseline and its 90% confidence interval at the geometric mean of the C_{max} for each dose. Additionally, the estimated slope with its 90% confidence interval will be provided. The used random coefficient model is based on Garnett et al. 2016 (12) with $\Delta QTcF$ as response variable, centered baseline QTc and plasma concentration as continuous covariates, treatment and time as fixed categorical effects, and a random intercept and slope for each subject. For more details refer to [Section 9.3](#).

For visualization, the BI 705564 plasma concentration against the response will be plotted as well as the (fixed effect) regression line, its 90% confidence interval and the geometric mean of C_{max} for each dose. For each subject and each time point, subtract the mean value of all individual observed ΔQTc values from the placebo group for this time point from the individual observed ΔQTc value for this subject and time point. This results in estimates for “individual $\Delta \Delta QTc$ ” values. These estimates will only be used for plotting purposes.

To check model assumptions, the conditional residuals will be plotted and presented in the statistical Appendix. In case of non-linearity or if there is evidence for a delayed effect, further models will be explored that better characterise the PK/ECG relationship (log(concentration), effect compartment, non-linear model etc.).

All of the above described graphical and statistical analyses will be also performed for HR in place of QTcF.

Appropriateness of heart rate correction methods of QT interval

To evaluate the appropriateness of the correction methods, the slope of the relationship of QTcF interval versus RR interval (values log-transformed using the natural logarithm) will be estimated by applying the random coefficient model described in [Section 9.3](#) using all time points. A scatterplot of QTcF vs RR including the estimated regression line will be included in the statistical Appendix of the CTR. The resulting (fixed effect) slope together with two-sided 95% confidence intervals will be included in this plot.

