##### **Food effect part**

Safety and tolerability of the investigational drug will be assessed based on:

- Adverse events (including clinically relevant findings from the physical examination)
- Safety laboratory tests
- 12-lead ECG
- Vital signs (blood pressure, pulse rate)

These parameters will be evaluated in a descriptive way only, and are therefore considered to be 'further parameters of interest'. A confirmatory analysis is not planned (see [Section 7.3](#)).

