## **7.3 PLANNED ANALYSES**

All individual data will be listed.

Adherence to the protocol (such as inclusion/exclusion criteria, times of measurement, compliance with intake of trial medication, treatment dispensing errors, prohibited concomitant medication, completeness and consistency of data) will be checked. Important protocol violations (IPVs) will be identified no later than in the Report Planning Meeting and provided in the TSAP.

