### **7.3.4 Safety analyses**

Safety will be assessed for the endpoints listed in [Section 5.2.1](#). All treated subjects (i.e., all subjects who received at least one dose of study drug), will be included in the safety analysis. Safety analyses will be descriptive in nature and will be based on BI standards. No hypothesis testing is planned.

The analyses will be done by 'treatment at onset'.

Treatments will be compared in a descriptive way.

In the single rising dose parts, the placebo control group in the safety evaluation will consist of all placebo treated subjects, regardless of the dose group in which they were treated and regardless of whether they participated in the single rising dose part under fed or under fasting conditions; the active treatment groups will be compared to the placebo group in a descriptive way. To explore potential differences between placebo subjects under fasting and under fed conditions, these two subgroups will be compared descriptively.

In all (single rising dose – fasting and fed - and food effect) parts, tabulations of frequencies/proportions will be used for the evaluation of categorical (qualitative) data, and tabulations of descriptive statistics will be used to analyse continuous (quantitative) data.

Measurements (such as ECG, vital signs, or laboratory parameters) or AEs will be assigned to treatments (see [Section 4.1](#)) based on the actual treatment at the planned time of the measurement or on the recorded time of AE onset (concept of treatment emergent AEs).

Therefore, measurements planned or AEs recorded prior to first intake of trial medication will be assigned to 'screening', those between first trial medication intake until the end of trial visit will be assigned to the treatment period. These assignments including the corresponding time intervals will be defined in detail in the TSAP. Please note that AEs occurring after the last per protocol contact but entered before database lock will be reported to drug safety only and will not be captured in the trial database.

Additionally, further treatment intervals (analysing treatments) may be defined in order to provide summary statistics for time intervals, such as combined treatments, on-treatment totals or periods without treatment effects (such as screening and post-study intervals).

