Adverse events will be coded using the Medical Dictionary for Regulatory Activities (MedDRA). Frequency, severity and causal relationship of AEs will be tabulated by treatment, system organ class and preferred term. SAEs, AESIs (see [Section 5.2.2.1](#)) and other significant AEs (according to ICH E3) will be listed separately.

Laboratory data will be compared to their reference ranges. Values outside the reference range as well as values defined as clinically relevant will be highlighted in the listings. Additionally, differences from baseline will be evaluated.

Vital signs or other safety-relevant data observed at screening, baseline, during the course of the trial and at the end-of-trial evaluation will be assessed with regard to possible changes compared to findings before start of treatment.

For the single rising dose parts (under fasting and fed conditions) of the study, a centralised evaluation of all 12-lead ECGs recordings (see [Section 5.2.4](#)) will be the basis for the derivation of further ECG parameters based on the ECG variables QT, HR, QTcF, QTcB, PR, QRS, and RR. The baseline value of an ECG variable is defined as the mean of the triple ECG measurements prior to drug administration. The derivation of the quantitative and qualitative ECG endpoints and their analyses will be described in the TSAP.

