4. CHANGES IN THE PLANNED ANALYSIS OF THE STUDY

All analyses as planned in the CTP will be performed and are described in more detail in this TSAP.

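### SAP 7.8.4 confines the 12-lead ECG listings and summaries to the rising-dose parts, against the protocol's commitments for the food effect part and the SAP's own general rules

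*SAP*

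**What the plan says.** **Protocol.** Section 5.2.1 gives the food effect part its own list of safety parameters, in which the 12-lead ECG is a separate item from adverse events. It adds: "These parameters will be evaluated in a descriptive way only". Section 7.3 opens with "All individual data will be listed", and excepts no part. Section 7.3.4 sets the form of the safety tables. "In all (single rising dose – fasting and fed - and food effect) parts", categorical data get frequency tables and "tabulations of descriptive statistics will be used to analyse continuous (quantitative) data". Later in the same section, after describing the central ECG evaluation in the rising-dose parts, it says: "The derivation of the quantitative and qualitative ECG endpoints and their analyses will be described in the TSAP".

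**SAP.** Section 4 states: "All analyses as planned in the CTP will be performed and are described in more detail in this TSAP". Section 5.2.2 repeats 12-lead ECG as a criterion without limiting it to any part, although it does limit continuous monitoring to the rising-dose parts. Section 7.8.4 has a heading for the 12-lead ECG that covers both the rising-dose parts and the food effect part. Under it stands one rule that reaches the food effect part: "Abnormal findings will be reported as baseline conditions (at screening) or as AEs (during the trial) if judged clinically relevant by the investigator". Then comes "The following ECG analyses will only be performed in the SRD parts", followed by the individual listing, the categorical tables, the descriptive statistics and the exposure-response models.

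**Elsewhere in the SAP.** Section 6.1 says that tables of vital signs, ECG and laboratory values are presented by on-treatment phase, and defines those phases for the food effect part as well. Section 7 promises a listing of individual values for all food effect subjects in Appendix 16.2. Neither is limited to the rising-dose parts.

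**The concern.** An analysis that the protocol plans for all parts is excluded for one of them by an explicit sentence in the SAP, while the SAP says nothing has changed. The SAP also contradicts itself: a programmer following 7.8.4 would produce no food effect ECG output, and one following Sections 6.1 and 7 would produce it.

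At stake is the visibility of interval changes that no investigator judged clinically relevant. The food effect part gives the only planned fed-versus-fasting ECG comparison within subjects at a fixed dose, since protocol 3.3 bars subjects treated in the fasting rising-dose part from the fed one. It is also the only source of ECGs at 10 mg fed, because the fed rising-dose part starts at 20 mg.

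**Working it through.** The plan states no figure on this point, so the check is mainly a comparison of texts.

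**1. What does the protocol limit to the rising-dose parts?** Protocol 5.2.4.1 limits the central reading of the 12-lead ECGs, and 7.3.4 limits the variables derived from that reading. SAP 6.7 confirms that no central reading is planned for the food effect part. Neither text withdraws the listing commitment in 7.3, the descriptive evaluation in 5.2.1 or the all-parts tabulation in 7.3.4.

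**2. What does SAP 7.8.4 leave for the food effect part?** Only the reporting of clinically relevant abnormal findings. The listing, frequency tables and descriptive statistics all stand below the restricting sentence.

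**3. Could the general rules in SAP 6.1 and 7 be followed as they stand?** A listing could. A table of changes from baseline could not. SAP 6.7 defines the ECG baseline only as the mean of the triplicate pre-dose recordings, whereas protocol 5.2.4.1 plans single ECGs in the food effect part. The per-period baseline in 6.7 covers vital signs and PK parameters, not ECG.

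**4. How many recordings are affected?** Flow Chart 2 schedules ECGs pre-dose and at 1, 2, 4, 8 and 24 h, which is 6 per period. With 12 subjects completing both periods and single recordings:
- in-period: 12 x 2 x 6 = 144
- pre-dose: 12 x 2 x 1 = 24
- post-dose: 144 - 24 = 120
- with one screening and one end-of-trial ECG per subject: 144 + 12 + 12 = 168

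The food effect subjects are 12 of the 92 planned (13%).

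**5. Could such a summary show anything?** The documents give no within-subject ECG variability, so this step is illustrative. Let s be the SD of a single QTcF reading within a subject, with independent errors. The fed-minus-fasting difference in change from pre-dose uses four readings per subject, so its variance is 4s² and the standard error of the mean over 12 subjects is √(4s²/12).

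| Assumed s (ms) | Standard error (ms) |
|---|---|
| 5 | 2.9 |
| 6 | 3.5 |
| 7 | 4.0 |

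That would serve a rough descriptive check at each time point. Local readings may vary more than assumed here, and the finding does not depend on these values.

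**The case against.** The strongest counter-argument is that the protocol itself planned this split. The synopsis words the food effect criterion as adverse events including relevant ECG findings, interval measurement is tied to the central reading, and 7.3.4 hands the ECG endpoints over to the SAP. On that view the adverse event tables satisfy the descriptive commitment, and Section 4 is not wrong. It can be added that the sentence in 7.3.4 naming ECG concerns the assignment of measurements to treatments, while the one on continuous data names no ECG variable.

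This does not carry. The synopsis uses the same wording for the rising-dose parts, where the ECG is nevertheless fully analysed. Section 5.2.1 lists the ECG apart from adverse events. The hand-over to the SAP follows the passage on central reading in the rising-dose parts and exempts nothing else. It is true that 7.3.4 does not spell out food effect interval tables, but the listing commitment in 7.3 is unqualified.

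Other objections stand. Protocol 5.2.4.1 names QT and QTcB as the values produced by the machines, so QTcF would have to be derived. The visible text does not say whether local interval values enter the trial database. Without placebo, a fed-minus-fasting difference cannot separate the effect of the meal from that of the drug. The rising-dose parts supply centrally read ECGs with placebo and higher doses, fasting to 80 mg and fed to 160 mg.

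**Conclusion.** The conflict is real. SAP 7.8.4 narrows what the protocol plans for the food effect ECGs, clashes with SAP 6.1 and 7, and makes the no-change statement in Section 4 inaccurate. It should be corrected, because the analysis is excluded by an explicit sentence and not merely left undetailed.

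A reader might infer that food effect ECGs go unreported altogether, or that the safety objective of that part fails for ECG. The documents do not support either. Clinically relevant findings are still reported, the general SAP rules point towards listing and tabulating the data, and descriptive safety is only an additional objective there (protocol 7.1.1).

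The practical impact is modest: 144 scheduled in-period recordings, assuming 12 completers and single ECGs, for a non-primary safety parameter at one dose. Parts of the SAP are removed from the public version, so the full ECG endpoint definitions cannot be seen. The restricting sentence is nevertheless clear as it stands.

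**What to change.** - **SAP 7.8.4:** add for the food effect part a listing of the locally read HR, PR, QRS and QT, with QTcF derived from local QT and RR where available. Add descriptive statistics by treatment for the change from the pre-dose ECG of the same period. Label both as locally read. No central reading is needed.
- **SAP 6.7:** define the food effect ECG baseline as the single pre-dose ECG of each period, and say what applies if the option of three ECGs per time point is used.
- **SAP 6.1 and 7:** align 7.8.4 with the general rules on ECG tables and food effect listings. If the local values cannot be obtained, declare and justify the omission in Section 4 and limit those general rules accordingly.

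The cost is one listing, one standard table and possibly a transfer of locally stored values. The drawbacks are that single local readings are noisier than the central ones and that the comparison has no placebo, so the output should be presented as descriptive only.

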**(3) Single rising dose part under *fed* conditions**

Visit	Day	Planned time (relative to drug administration) [h:min]	Approximate clock time of actual day [h:min]	Event and comment	Safety laboratory	PK  blood	PK  urine			12-lead ECG	Continuous ECG monitoring	Vital signs (BP, PR)	Questioning for AEs and concomitant therapy 
1	-21 to -1			Screening (SCR) 	x					x		x	
2	-3 to -1	-72:00 	08:00	Ambulatory visit	x								x
	1	-2:00	06:00	Admission to trial site  , allocation to treatment 	x 	x 	x 			x 	x 	x 	x 
		-0:30	07:30	High fat, high calorie breakfast									
		0:00	08:00	Drug administration			▲				▲		
		0:30	08:30			x				x 		x	x
		1:00	09:00			x				x 		x	x
		1:30	09:30			x				x 		x	
		2:00	10:00	240 mL fluid intake		x				x 		x	x
		3:00	11:00			x				x 		x	x
		4:00	12:00	240 mL fluid intake, thereafter lunch 	x	x	+			x 	▼	x	x
		6:00	14:00			x				x 		x	x
		8:00	16:00	Snack (voluntary) 		x	+			x 		x	x
		10:00	18:00			x							
		11:00	19:00	Dinner									
		12:00	20:00			x	+			x 		x	x
	2	24:00	08:00	Discharge from trial site, breakfast  (voluntary)	x	x	▼			x 		x	x
		34:00	18:00	Ambulatory visit		x						x	x
	3	48:00	08:00	Ambulatory visit	x	x				x 		x	x
	4	72:00	08:00	Ambulatory visit		x				x 		x	x
	6	120:00	08:00	Ambulatory visit									x 
	8	168:00	08:00	Ambulatory visit	x								x
	10	216:00	08:00	Ambulatory visit									x
4	11 to 15			End of trial (EOT) examination 	x					x		x	x

1. Subject must be informed and written informed consent obtained prior to starting any screening procedures. Screening procedures include physical examination, check of vital signs, ECG (including rhythm strip of at least 15 minutes), safety laboratory (including drug screening), demographics (including determination of body height and weight, smoking status and alcohol history), relevant medical history, concomitant therapy and review of inclusion/exclusion criteria. Pharmacogenetic samples will be collected, if needed.

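### The first-step check for a delayed effect on QTcF and heart rate plots change from baseline without placebo correction, so shared meal and time-of-day changes can mimic or mask a lag in that display

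*SAP*

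**What the plan says.** In SAP 7.8.4 (Quantitative endpoints), the first exposure-response step is that "it is investigated if there is a potential delayed or accelerated (e.g. metabolites) effect of the drug on QTcF". The method is "overlaying time profiles of plasma concentrations and QTcF changes from baseline", offered as a general visual impression. The figures are to "be generated for each subject (presented in statistical Appendix of the CTR), as well as for means per active treatment". Heart rate follows: "All of the above described graphical and statistical analyses will be also performed for HR in place of QTcF".

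Three later elements bear on the same question:

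- **The model.** A random coefficient model is fitted separately for fasting and fed doses. It has baseline and concentration as covariates, fixed effects for treatment and time, and placebo subjects at zero concentration.
- **Placebo-subtracted values.** In describing the concentration-versus-response plot, the SAP defines individual values from which the placebo mean at the same time point is subtracted. It adds: "These estimates will only be used for plotting purposes".
- **What evidence of delay leads to.** After the residual plots, the SAP states: "In case of non-linearity or if there is evidence for a delayed effect, further models will be explored". An effect compartment is one example given.

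Baseline is the mean of one pre-dose triplicate (SAP 6.7), planned at -2:00. Protocol Flow Chart 3 places the "High fat, high calorie breakfast" at -0:30. In both single rising dose parts lunch follows the 4 h measurements, a voluntary snack is offered at 8 h, and dinner is at 11 h.

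**The concern.** The step asks about the effect of the drug, but the plotted quantity is the drug effect plus everything else that has changed since a single early-morning baseline. Subjects on active drug and on placebo share the meals and the time of day. Those influences have their own time course, which need not follow the concentration curve. In the fed part, breakfast falls between the planned baseline and every on-treatment ECG. In the fasting part the shared influences are time of day and, after 4 h, lunch.

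A single pre-dose baseline cannot remove such changes; a concurrent placebo group can. Without it, a direct effect may appear delayed, prompting an unneeded extra model. A delayed effect may also appear direct, so that attention stays on the estimate at the geometric mean of Cmax, where a delayed effect is not at its largest.

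**Working it through.** The plan gives no figure for this check, so there is nothing to reproduce. The documents supply the ECG times, the meal times, 6 active and 2 placebo subjects per dose group, and hence 6 x 2 = 12 placebo subjects fasting and 4 x 2 = 8 fed. Every effect size, rate constant and SD below is an assumption.

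**1. No drug effect, fed part.** Let hours since breakfast be m = t + 0.5, and let the meal shift be e(t) = A x (m/2) x exp(1 - m/2), with A = -5 or -8 ms. Concentration is proportional to exp(-0.12t) - exp(-0.5t), which peaks at ln(0.5/0.12)/(0.5 - 0.12) = 3.8 h.

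| Time | Concentration / Cmax | e(t), A = -5 | e(t), A = -8 |
|---|---|---|---|
| 1.5 h (rising) | 0.75 | -5.0 ms | -8.0 ms |
| 8 h (falling) | 0.75 | -0.8 ms | -1.3 ms |

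At equal concentration, mean change differs by 5.0 - 0.8 = 4.2 ms to 8.0 - 1.3 = 6.7 ms. On the overlay this resembles hysteresis. After placebo subtraction the expected difference is zero.

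**2. Displaced peaks.** Take drug effects of 5 or 10 ms at the planned ECG times, with rate constants (ka, ke) of (1.5, 0.15) or (0.7, 0.1) per hour. The shared change is either an early dip or rise of size A centred at 1.5 h, -/+A x exp(-((t - 1.5)/1.5)^2), or a 24-hour cosine that is zero at -2 h, +/-A x (1 - cos(2 pi (t + 2)/24))/2. A is 2, 5 or 10 ms. The delayed effect uses an effect-compartment rate of 0.3 per hour.

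| True effect peak | Shared change | Peak seen in raw change |
|---|---|---|
| Direct, 1.5 h | early dip | 3 to 4 h |
| Direct, 1.5 h | time-of-day rise | 2 to 8 h |
| Direct, 3 h | early dip | 4 to 6 h |
| Direct, 3 h | time-of-day rise | 4 to 8 h |
| Delayed, 6 h | early rise | 6 h (unmoved) at A = 2; 1.5 to 2 h at A = 5 or 10 |
| Delayed, 6 h | time-of-day fall | 2 to 4 h |
| Delayed, 8 h | early rise | 8 h (unmoved) at A = 2; 1.5 to 2 h at A = 5 or 10, except 8 h for a 10 ms effect with A = 5 |
| Delayed, 8 h | time-of-day fall | 4 to 6 h; 24 h in one extreme case |

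With A = 0 nothing moves. With the placebo course subtracted, the peak returns to its true time in every case.

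**3. Cost in precision.** The SE ratio for a dose-group mean is sqrt(1/6 + 1/n)/sqrt(1/6).

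- Fasting, n = 12: sqrt(1.5) = 1.22.
- Fed, n = 8: sqrt(1.75) = 1.32.
- With an assumed SD of 8 ms: 8/sqrt(6) = 3.3 ms uncorrected, 8 x sqrt(1/6 + 1/12) = 4.0 ms fasting, and 8 x sqrt(1/6 + 1/8) = 4.3 ms fed.

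A loop compares two time points, so its SE is multiplied by sqrt(2(1 - r)). For an assumed correlation r of 0.5 down to 0, the fed loop SE goes from 3.3-4.6 ms uncorrected to 4.3-6.1 ms corrected. The 8-subject placebo mean alone contributes 2.8-4.0 ms, and the same placebo mean enters all four fed groups.

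**The case against.** A reader might infer that the overlay decides which model is used, so that a false lag replaces the direct-effect model. The SAP does not say that. It offers the overlay as a visual impression, does not tie the trigger to that display alone, and says that further models are explored. Residuals from a model with time effects and placebo data are also examined, and the direct-effect model is nowhere said to be dropped.

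A reader might also infer that the reported slope and drug-placebo differences are distorted. The time effects and placebo data protect those estimates against shared time courses, provided the drug effect is direct. If the effect is delayed, the protection is weaker. About 75% of the subjects informing the common time effects are on active drug (36 of 48 fasting, 24 of 32 fed), so part of a delayed effect can be absorbed there and the residuals become less revealing.

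Other points on the plan's side also stand. Mean change profiles are shown by treatment, so placebo can be compared by eye, though not on the concentration overlay. A shared meal pattern should recur at every dose, whereas a drug lag should scale with dose. The restriction to plotting does not exclude use in the overlay, which is itself a plot. Section 9.3, cited for model details, is not in the available text, so a correction there can be neither confirmed nor ruled out. Finally, subtraction adds noise comparable with the assumed 4 to 7 ms artefact, and a group mean does not remove an individual's own meal response. These points limit the concern and shape the remedy, but they do not make uncorrected change the right quantity for a question about the drug's own time course.

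**Conclusion.** The concern holds as a limited one. The stated first look for a lag in QTcF and heart rate uses a quantity in which shared meal and time-of-day changes are mixed with the drug effect, and these can mimic or mask a delay. The weakness is confined to one exploratory display, which is one input to whether further models are explored. Residual plots and by-treatment profiles give partial protection.

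The practical size cannot be derived from the documents: the 4 to 7 ms figure and the displaced peaks rest wholly on assumed effects. The breakfast argument applies only to the fed part. It also relies on the planned -2:00 baseline, since pre-dose procedures may be completed at any time within 3 h before dosing.

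**What to change.** Add a sentence to SAP 7.8.4. For each active dose group, overlay mean concentration with mean change from baseline minus the mean change, at the same time point, of the placebo group from the same part (Placebo fast or Placebo fed), for QTcF and for heart rate. Show the raw active and placebo mean change profiles alongside, so that a chance fluctuation in the small shared placebo group can be recognised. Keep the per-subject overlays as supportive displays.

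The programming cost is small because the SAP already calls for time-matched placebo means. The statistical cost is the 1.22-fold (fasting) or 1.32-fold (fed) rise in the standard error of group means, and placebo noise common to all dose groups within a part.
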